Next, participants will undergo a moderate psychological stress adapted from the commonly used Trier Social Stress Test (TSST)³³. The TSST protocol has been adapted for use in recalling race-related experiences³⁴ underscoring its appropriateness for our protocol. [name] (Co-Investigator) and colleagues, have also used a similar experimental protocol and will provide related expertise for this project.^{35,36} Participants will be asked to recount one real-life stressful situations; one event will be a stressful race-related event and one event will be a stressful event that is not race-related. We will randomize participants such that half will recall the racial experience and half will recall the non-racialized stressful event. Each participant will have an equal chance of being placed in the racialized or non-racialized experience group. The Project Coordinator will provide instructions using a script. Participants will be given two minutes to prepare their statement, and three minutes to deliver the statement. There will be an 'audience' present at each participant's speaking task. Aligning with previously conducted involving audiences^{33,35-38}, each audience will include two observers who are of same race as the participant (African American), to heighten stress responses. Observers will wear white coats, and will be trained on the study protocol such that their behaviors are identical for each

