manipulation task. The audience will be trained to remain neutral during the task, told to not show empathy and not to smile at any time during the test. Observers have not yet been identified, however once determined, the individuals serving as observers will obtain a CITI certification, and study staff will submit observer credentialing as amendment modification to the protocol. The project coordinator will also remain in the room while participants recall each designated stressful experience. Blood pressure readings will be taken every 1 minute during the participant's preparation time and the actual recall task. The participant will be expected to use the entire three minutes for recall in each exercise; the project coordinator will cue the participant to continue until the 3-minute mark via standardized prompts from a script. Participants will be asked to rate their level of distress caused by the stressful event using an adapted version of Cooper's racism recall scale.³⁴ and again rate their level of distress on a linear scale (0 to 100) using the SUDS³². Participants will undergo a 45-minute recovery period after the first recall task; blood pressure readings will be taken every 5 minutes during this period. Immediately following the first 45-minutes of recovery, participants will provide a third blood draw (6 mL). Participants will undergo another 45-minutes of recovery, and provide and one final blood draw (6 mL) at the conclusion of the recovery period.

Over the course of the study, participants will provide 3, 4 mL samples of blood and 3, 6mL samples of blood. A total of up to 30 mL may be taken over the course of the study. The project coordinator will debrief participants on the purpose of the experimental manipulation and common reactions to it. Participants will also be debriefed on the entire experimental manipulation experience, including the audience's purpose. Participants will be paid \$150 at the conclusion of Day 2 (\$50 for return of ABPM and \$100 for completion of experimental manipulation). The experimental protocol along with data time points are outlined in Figure 2.

Data Sources

Participants will be asked to provide data from the following sources:

- **Cross-sectional survey data** that are provided by completing the CAPI (see attached)
- **Medical chart data**, used only to verify their last eGFR in order to achieve equal numbers of participants by study stage/CKD diagnosis

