The consent process will be conducted in-person by the study staff, in a private location near the waiting room in order to maximize convenience and privacy for the participant. An IRB-approved written informed consent will be obtained from each participant at entry into the study; elements of informed consent will include: (a) participant reviews the study consent form; (b) investigator(s) or study staff review the consent with participants to confirm understanding and answer any pending questions; and (c) participant signs the consent form once the investigator(s) or study staff are convinced that the protocol is understood. Key elements of the consent form describe the voluntary nature of study participation, clarification that the decision to join or not join the research study will not affect the participant's status as a patient, and that participants are free to withdraw at any point in time. The consent form includes a standard HIPAA Authorization document as well. After signing the consent form, participants will be given a hard copy of the form for their own records. Please see the attached consent form for details.

IV. Potential Risks/Discomforts to Study Participants and measures to prevent occurrence

Possible risks are related to:

1. CAPI: Being asked questions about the stress in participants' lives may cause them to have unpleasant and/or upsetting feelings.
2. Intravenous catheter: This can result in infection, bruising of the skin, or a blood clot in the vein. Participants may have some discomfort from the blood drawing. The risk from blood drawing is minimal, but may include bruising and infection.
3. Experimental manipulation: Recalling an upsetting experience may be unpleasant.
4. Blood pressure monitoring: Wearing the ABPM throughout the day and night may be inconvenient for participants, and some people may experience sleep disturbance while wearing the device at night. Some individuals might also experience some bruising where the cuff is located.

V. Benefits

Participants may not derive personal benefit from their involvement in this study. However, participants may find some of the information they receive from this study helpful. For example, participants will receive a detailed report of their nocturnal blood pressure after wearing the ABPM device. Participants with healthy reports may use this information to continue healthy practices, and participants with concerning reports may use this information to seek professional

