Stopping Rules for Stress-Inducing Experimental Manipulation

Absolute Indications for Termination

- Drop in systolic blood pressure >10 mm Hg (persistently below baseline).
- Technical difficulties monitoring blood pressure. [SEP]

Relative Indications for Termination [SEP]

- Increasing chest pain. [SEP]
- Participant becomes excessively anxious, uncomfortable, or requests to stop.
- Fatigue, shortness of breath, wheezing, leg cramps, or claudication. [SEP]
- Hypertensive response (systolic blood pressure >200 mm Hg and/or diastolic blood pressure >92 mm [SEP]Hg).

Patient reporting rules for blood pressure

[name] (Co-Investigator and nephrologist) will review all participants' blood pressure readings from the 24-hour ABPM task. Participants with healthy / normal blood pressure readings (readings \leq 170/110 mm Hg) will be notified of these numbers via mail from [name] along with information about what the readings mean for their health. The project coordinator will immediately alert [name] of participants with blood pressure readings that may be concerning (>170/110 mm Hg). [name] will review associated readings, and notify the participants via phone at her discretion. All participants will have the nocturnal blood pressure readings incorporated into their personal health records; nephrology clinic staff will be responsible for integrating these numbers into participants' electronic health records within the nephrology clinic.

Patient safety data examination, monitoring procedures/oversight. All adverse events (AEs) will be graded as to their attribution (unrelated to protocol, or possibly, probably, or definitely related to protocol). Any AE that is reported to either the PI or her designated research associates by a study participant or by medical staff caring for the participant and which meets the criteria will be documented as such. Potential ("expected") AEs are described above under "Potential Risks". Serious adverse events (SAEs) are predefined as: any experience that suggests a significant hazard, such as events which: a) are fatal, b) are life threatening, c) result in permanent disability, d) require inpatient hospitalization, or e) involve cancer, a congenital anomaly, or drug overdose. The standard Emory IRB reporting guidelines for AEs and SAEs will

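### A participant's request to stop the stress task is listed only as a relative ground for ending it, which does not fit the unqualified right to withdraw

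*Combined protocol and SAP*

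**What the plan says.** Section X, under the stopping rules for the stress manipulation, gives two lists. The one headed "Absolute Indications for Termination" has two items: a persistent fall in systolic pressure of more than 10 mm Hg, and a fault in blood-pressure monitoring. The one headed "Relative Indications for Termination" holds several clinical signs and the bullet "Participant becomes excessively anxious, uncomfortable, or requests to stop". Neither term is defined.

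Section III.F (Informed Consent Process) says the consent form tells patients that "participants are free to withdraw at any point in time". It makes no exception for any procedure.

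Section III.E (Day 2) sets out the task: "Participants will be given two minutes to prepare their statement, and three minutes to deliver the statement". On the recall part it adds: "The participant will be expected to use the entire three minutes for recall in each exercise", and "the project coordinator will cue the participant to continue until the 3-minute mark via standardized prompts from a script". It does not say what happens to the prompts if the participant asks to stop.

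Section IX provides for training specific to the study, and Section X has medical staff present during the manipulation.

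**The concern.** Two headings serve a purpose only if they call for different responses. The plain contrast is that an absolute indication ends the task and a relative one is weighed. On that reading a monitoring fault must end the task, while a participant's request to stop is something for staff to consider.

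The bullet also joins two different things. Whether someone is excessively anxious or uncomfortable needs judgement. Whether someone has asked to stop does not.

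The setting makes clear wording more useful. The task is meant to cause distress, the observers are trained to stay neutral, and the coordinator prompts the participant to fill the recall time. None of this is improper. What is at stake is participant protection and agreement between sections of the protocol. Sample size, power and type I error are not involved.

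**Working it through.** The plan gives no figure to reproduce here. The check is a comparison of text, followed by a count of the data lost when a participant does stop.

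**Comparison**

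| Question | Where | What it gives |
|---|---|---|
| Is a request an absolute indication? | Section X, absolute list | No. Both items concern blood pressure or its monitoring. |
| Is it a relative indication? | Section X, relative list | Yes, in one bullet with anxiety and discomfort. |
| Is the right to withdraw limited in time or by procedure? | Section III.F | No. |
| Do the prompts end on a request? | Section III.E, Day 2 | Not stated. |

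1. A right that holds at any time holds during the task, which lasts 2 + 3 = 5 minutes.
2. A request made in those minutes therefore falls under an unqualified right.
3. The only stopping rule that mentions such a request places it in the list which, on the ordinary reading, is discretionary.
4. No section of the supplied document says that a request always ends the task.

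Stopping at every request satisfies both sections. Treating the request as one factor to weigh could be defended from Section X but not from Section III.F. The two sections can be followed together, but the stopping rule does not require staff to do so.

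**Data lost when a participant stops**

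Inputs: one blood-pressure reading per minute in preparation and recall (Section III.E, Day 2 and item viii); in the recovery period that follows the recall, "blood pressure readings will be taken every 5 minutes during this period"; inflammatory samples before the task and at 45 and 90 minutes after it (item viii); reactivity defined as the recall mean minus the rest mean (item viii).

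- Task readings: 2 × 1 = 2 in preparation and 3 × 1 = 3 in recall, 5 in all.
- Stop during preparation: 0 of 3 recall readings, so no recall mean and no reactivity score.
- Stop during recall: between 0 and 3 of the 3 readings remain, and a mean exists only if at least 1 was taken.
- Participant also leaves the session: 45/5 = 9 recovery readings are lost if the five-minute schedule covers only the first 45 minutes, or 90/5 = 18 if it covers both periods. The 45- and 90-minute samples are lost too, which is 2 of 3 inflammatory time points.
- Participant stops the task but stays: the recovery readings and both later samples can still be collected.

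**The case against.** The best reply is that there is no contradiction. Section III.F concerns leaving the study and Section X concerns ending a task, and nothing in Section X limits the right to leave. Because relative is undefined, reading it as discretionary is an inference. The cue to continue reads most naturally as help for someone who has run out of things to say. The prompt script and the consent form were not available, and either could say that a request ends the task. Training and medical staff are provided for.

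Much of this stands. The point is an ambiguity, not a proven conflict in conduct, and the silence of the Day 2 text about the prompts is only supporting evidence. The data losses follow from any stop, which Section III.F already permits. They become a cost of the rewording only if staff would otherwise have continued, and nothing shows that they would.

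The objection does not remove the main point. Withdrawal at any time includes the minutes of the task. If relative carries no discretion, the two headings have no purpose. No part of the supplied text makes a request binding, and the protocol does not say what the training teaches about such requests.

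**Conclusion.** The point holds and is minor. Section X places a participant's request to stop in a list that is ordinarily read as discretionary, and this does not fit the unqualified right in Section III.F.

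The placement of the words is certain. Their effect rests on two assumptions: that relative carries its ordinary meaning, and that the unseen script and consent form do not already settle the matter. The documents give no rate of requests to stop, so the number affected lies somewhere between 0 and the 100 enrolled. No estimate, test or power figure changes.

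**What to change.** 1. In the Section X stopping rules, move a participant's request to stop into the absolute list, ending the task immediately. Leave staff-judged excessive anxiety or discomfort in the relative list. The ranking of the clinical signs stays with the investigators. This is the essential change.
2. In the Day 2 text of Section III.E, state that the scripted prompts cease once a participant asks to stop, and check that the script agrees.
3. In the same place, state that someone who stops the task but is willing to stay may still give the recovery readings and the 45- and 90-minute samples. The inconsistency does not require this step, but it limits the data lost.

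The cost is one reworded bullet and one or two added sentences. The downside is a few incomplete tasks, and the existing right to withdraw already allows for these.

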Blood pressure readings captured during participants' 24-hour ABPM wear period will be reviewed once participants return the device. We anticipate these blood pressure readings to be beneficial knowledge to participants and their overall health plan, and as a result will retrospectively provide these readings to participants and their physician, as appropriate. The project coordinator will review all blood pressure readings upon return of the device, and relay all readings to [name] (Co-Investigator and nephrologist) for review. Potentially concerning readings (>170/110 mm Hg) will be flagged for immediate review, and [name] will contact participants with alarming readings by phone, as determined by her review. Participants with healthy / normal blood pressure readings may also benefit from this information, and as a result, will be notified of these numbers via mail from [name] along with information about what the readings mean for their health. All participants will have the 24-hour blood pressure readings incorporated into their personal health records; nephrology clinic staff will be responsible for integrating these numbers into participants' electronic health records within the nephrology clinic. Practices for reporting blood pressure readings will be outlined in the participant consent form (see attached).

Day 2: Experimental manipulation & ABPM return

Day 2 of data collection will take place at the Georgia Clinical and Translational Science Alliance (Georgia CTSA), Emory University Hospital Clinical Research site at the Atlanta Midtown location within a room with a door (see attached). All Day 2 data collection appointments will be scheduled between the hours of 9:00 AM and 11:00 AM to account for diurnal changes in inflammatory markers. First, participants will return the ABPM and the ABPM diary to the project coordinator.

[figure not shown]
Prior to initiating data collection on Day 2, study staff will retrieve a History & Physical (H&P) form from the participant's Emory physician. The H&P form is an official record of a physical from a physician, and must have been obtained within the past 30 days to confirm that patients are fit to participate in the study. Study staff will upload the H&P form into the CR-assist appointment system for easy retrieval at the participant's next visit. Participants will be

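### One cut-off, 170/110 mm Hg, is both the alert trigger and the top of the healthy/normal range for ambulatory readings, while a diastolic above 92 counts as hypertensive in the recall task

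*Combined protocol and SAP*

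**What the plan says.** Three places in the combined protocol and SAP matter.

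- **Section X, stopping rules for the experimental manipulation.** Under "Relative Indications for Termination" the list includes "Hypertensive response (systolic blood pressure >200 mm Hg and/or diastolic blood pressure >92 mm" Hg. This is separate from the absolute indications, so exceeding it leaves the decision to staff.
- **Section X, patient reporting rules for blood pressure.** One group is introduced as "Participants with healthy / normal blood pressure readings (readings" at or below the cut-off, and the rule continues: "170/110 mm Hg) will be notified of these numbers via mail". The mailing also explains what the numbers mean. The other group has "blood pressure readings that may be concerning (>170/110 mm Hg"), about which the project coordinator alerts the nephrologist co-investigator immediately.
- **Section III.E, Day 1 procedures.** The same alert limit appears: "Potentially concerning readings (>170/110 mm Hg) will be flagged for immediate review". The only other group is again the healthy/normal one, here without a number: "Participants with healthy / normal blood pressure readings may also benefit from this information".

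Both sections have the nephrologist review all ambulatory readings, and both provide for entry in the health record.

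**The concern.** A limit chosen to decide who needs an immediate call is not necessarily the limit below which a reading is normal. The plan uses 170/110 mm Hg for both purposes and leaves nothing in between. Any reading that does not trigger an alert is, by the written definition, healthy/normal. The stopping rules just above apply the word hypertensive to diastolic values well inside that range.

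What is at stake is what participants are told. Section V gives the label some weight: "Participants with healthy reports may use this information to continue healthy practices", whereas seeking professional counsel is mentioned only for those with concerning reports. Eighty of the 100 planned participants have CKD, and Section I names hypertension among the commonest causes of CKD. Values in the disputed band may well occur in this sample.

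**Working it through.** No power or sample-size figure is involved. The check sets the stated limits side by side.

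| | Recall task (Section X, stopping rules) | Ambulatory readings (Section X, reporting rules; alert limit also in III.E) | Task minus ambulatory |
|---|---|---|---|
| Diastolic, mm Hg | hypertensive above 92 | healthy/normal up to 110 | 92 − 110 = −18 |
| Systolic, mm Hg | hypertensive above 200 | concerning above 170 | 200 − 170 = +30 |
| Joined by | and/or | not stated | |
| Consequence | discretionary stop | letter, or immediate alert | |

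1. **Diastolic.** A value above 92 and up to 110 is a hypertensive response in the task. The same value on the monitor is healthy/normal, provided the systolic is not above 170. The band is 110 − 92 = 18 mm Hg wide.
2. **Systolic.** A value above 170 and up to 200 is concerning on the monitor but does not by itself meet the task definition. That band is 200 − 170 = 30 mm Hg wide.
3. **Direction.** The task limit is stricter on diastolic and looser on systolic. A general view that one setting calls for more caution than the other would move both limits the same way, so it does not explain the pattern. The documents offer no other explanation.
4. **And or or.** Take a reading of 150/115. If exceeding either number counts as concerning, it triggers an alert. If both must be exceeded, it does not. It also fails a healthy/normal definition that requires both numbers to be within the limit, and then it falls in neither group. The task rule states its connective; the ambulatory rule does not.
5. **Both rules can meet in one person.** The eligibility criteria in Section III.C set no blood pressure limit. A participant whose monitor shows a diastolic in the 18 mm Hg band could be classed as healthy/normal and, if the pressure is similar on Day 2, start the task already above the relative stopping limit.

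**The case against.** The best reply is that the two rules do different jobs. One guides staff during a supervised, provoked stressor; the other decides how quickly and by what route 24-hour results reach the participant. A value can justify caution in the first setting without justifying an urgent call in the second, and staff can follow both rules. This stands. A reader might infer that the rules are incompatible in operation, but the documents do not support that. The conflict lies in how the same value is labelled.

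The safeguards also stand. The nephrologist sees every participant's readings, flagged or not; results may go to the participant's physician; and readings enter the health record (Section III.E refers to the 24-hour readings, Section X to the nocturnal ones). The and/or gap therefore affects the speed and route of notice, not whether a nephrologist sees the reading.

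A reader might also infer that participants will be told in writing that raised pressure is healthy. The letter's wording is not in the documents, and the letter is to explain the numbers. Section V gives no numeric limit and speaks of continuing healthy practices, not of carrying on unchanged, so it is no independent evidence of conflict.

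None of this removes the definition itself. As written, healthy/normal extends to 170/110, and a letter drafted from the protocol could carry that label.

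**Conclusion.** The point holds as an inconsistency in classification and labelling that should be corrected. Its size, taken directly from the protocol, is an 18 mm Hg diastolic band with opposite labels, a 30 mm Hg difference in the other direction on systolic, and an undefined connective for 170/110. The participant-level consequence is a possibility, reduced by the nephrologist's review, and it depends on how the letter is worded.

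Two stronger readings are not supported. First, a reader might conclude that the diastolic limit will stop many tasks and cost Aim 2 reactivity data. The limit is discretionary, and the documents give no diastolic mean or standard deviation. The share of participants above 92 cannot be derived from them, and exceeding 92 is not the same as being stopped. Second, a reader might take 92 for a misprint because 200/92 does not pair as 170/110 does. Nothing in the documents requires the limits to pair or shows that a digit is wrong.

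**What to change.** The sponsor and the clinical investigator should reconcile Section III.E (Day 1) with the stopping and reporting rules in Section X:

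- Separate the trigger for immediate review from the healthy/normal label used in mailed reports, and say how readings that do not trigger review but are not considered normal will be described.
- Confirm that the task limits and the ambulatory limits are each as intended, and give the reason they differ.
- State whether 170 and 110 are joined by and or by or, so that every reading falls in exactly one group.
- Check the participant letter against the revised wording.

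The choice of limits is a clinical decision, and none is proposed here. The cost is a short protocol amendment and, where needed, a revised letter. Data collection and the statistical analysis are unaffected unless the limits themselves change.
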